#### 7.2.2. Proportion of Patients with SRI-5 Response at Each Visit

The SRI-5 is a composite index of SLE disease improvement that consists of scores derived from the SLEDAI-2K, the BILAG 2004 Index and the PGA. Response based on the SRI-5 is defined by:

1)  $\geq$  5-point reduction from baseline in SLEDAI-2K total score

AND

2) No new severe disease activity (BILAG A organ score) or more than 1 new moderate organ score (BILAG B) compared with baseline

AND

3) No deterioration from baseline in the PGA by  $\geq$  30mm.

The primary analysis described in Section 7.1.1 and Table 2 will be repeated for each nominal visit as described in Section 7.2.1 based on the SRI-5 response definition and will be presented by study phase and treatment group in the FAS. The 3 components will not be summarized separately by visit for SRI-5 response. Other analyses described in Section 7.1.1 may also be performed.

The denominators for analyses will be the number of patients in the FAS with an evaluable post-baseline SRI-5 assessment defined as those with data for PGA, SLEDAI-2K and BILAG (whether observed or imputed via LOCF depending on the analysis) at a given visit.

Statistical testing data will be omitted from MAD Phase 1b treatment group displays.

Sponsor: Boston Pharmaceuticals, Inc.  
Protocol Number: BOS161721-02  
SAP Version and Date: Version 4.0, 23Apr2021

### 7.2.3. Proportion of Patients with SRI-6 Response at Each Visit

The SRI-6 is a composite index of SLE disease improvement that consists of scores derived from the SLEDAI-2K, the BILAG 2004 Index and the PGA. Response based on the SRI-6 is defined by:

1)  $\geq$  6-point reduction from baseline in SLEDAI-2K total score

AND

2) No new severe disease activity (BILAG A organ score) or more than 1 new moderate organ score (BILAG B) compared with baseline

AND

3) No deterioration from baseline in the PGA by  $\geq$  30mm.

The primary analysis described in Section 7.1.1 and Table 2 will be repeated for each nominal visit as described in Section 7.2.1 based on the SRI-6 response definition and will be presented by study phase and treatment group in the FAS. The 3 components will not be summarized separately by visit for SRI-6 response. Other analyses described in Section 7.1.1 may also be performed.

The denominators for analyses will be the number of patients in the FAS with an evaluable post-baseline SRI-6 assessment defined as those with data for PGA, SLEDAI-2K and BILAG (whether observed or imputed via LOCF depending on the analysis) at a given visit.

Statistical testing data will be omitted from MAD Phase 1b treatment group displays.

### 7.2.4. Oral Corticosteroid (CS) Reduction

The average daily CS dose will be presented over time starting with Day 0 as baseline. Oral CS usage for all visits will be based on the average daily dose, defined as the sum of the corticosteroid doses taken each day from the date of the previous visit to the day before the date of the current visit (converted to prednisone equivalent dose) / the duration between the two visits. For example, the average daily dose at Day 0 (Baseline) is the sum of daily doses of CS from the screening visit to the day prior to Day 0 divided by the duration between the screening visit to the day prior to Day 0, inclusive. Similarly, the average daily dose at Day 30 is the sum of daily doses of CS from Day 0 to the day prior to Day 30 divided by the duration between Day 0 to the day prior to Day 30, inclusive. Partial dates for CS use will be imputed based on details in Section 5.5. Oral CS will be converted to prednisone dose equivalence for analysis of reduction of oral CS use. Common prednisone dose equivalents are provided in Table 3.

**Table 3**

| Medication          | Prednisone Dose Equivalence |
|----------------------------|------------------------------------|
| Prednisone                 | 1 mg                               |
| Cortisone                  | 5 mg                               |
| Hydrocortisone             | 4 mg                               |
| Deflazacort                | 1.2 mg                             |
| Meprednisone               | 1 mg                               |
| Prednisolone               | 1 mg                               |
| Methylprednisolone         | 0.8 mg                             |
| Methylprednisolone Acetate | 0.8 mg                             |
| Triamcinolone              | 0.8 mg                             |
| Triamcinolone Acetonide    | 0.8 mg                             |
| Budesonide                 | 0.25 mg                            |
| Dexamethasone              | 0.16 mg                            |
| Bethamethasone             | 0.16 mg                            |

#### 7.2.4.1. Proportion of Patients with a sustained reduction of oral CS between Day 120 and Day 210 (MAD)

The proportion of patients with a sustained reduction of oral corticosteroid, defined as  $\leq 10$  mg/day prednisone equivalent and  $<$  Day 0 dose, between Day 120 and Day 210 determined based on actual daily CS usage on and in between the nominal visit dates will be summarized for MAD Phase 1b by treatment group in the FAS. To qualify as sustained reduction, the actual daily CS usage needs to meet the definition above every day between nominal visit dates for Day 120 and Day 210 inclusive. LOCF and imputation for missing values will not be performed. Otherwise, statistical methods described in Section 7.1.1 will be implemented. Patients who withdraw prior to Day 210 or are designated as a medication failure on or prior to Day 210 or miss the Day 120 and/or the day 210 visit will not be considered to have sustained reduction in CS. Denominators for percentages are the number of patients taking oral CS at baseline.

#### 7.2.4.2. Proportion of Patients with a sustained reduction of CS between Day 150 and Day 210 (POC)

The proportion of patients with a sustained reduction of oral corticosteroid, defined as  $\leq 7.5$  mg/day prednisone equivalent and  $<$  Day 0 dose, between Day 150 and Day 210 determined based on actual daily CS usage on and in between the nominal visit dates will be summarized for POC Phase 2 by treatment group in the FAS. To qualify as sustained reduction, the actual daily CS usage needs to meet the definition above every day between nominal visit dates for Day 150 and Day 210 inclusive. LOCF and imputation for missing values will not be performed. Otherwise, statistical methods described in Section 7.1.1 will be implemented. Patients who withdraw prior to Day 210 or are designated as a medication failure on or prior to Day 210 or miss the Day 150 and/or Day 210 visit will not be considered to have sustained reduction in CS. Denominators for percentages are the number of patients taking oral CS at baseline.

#### 7.2.4.3. Percent Reduction in CS Administration from Day 0 through Day 210 (POC)

The percent reduction in CS administration from Day 0 through Day 210 determined based on the average daily CS usage will be summarized for POC Phase 2 by treatment group and visit. Average daily dose will be calculated for nominal visits as defined in Section 7.2.4. This will be performed for patients in the FAS who received  $\geq 7.5$  mg/day prednisone equivalent at Day 0. Patients considered medication failures will be excluded from the percent reduction analysis at timepoints on and after the first date of medication failure.

#### 7.2.5. Proportion of new or recurrent BILAG A flare or $>1$ BILAG B flare through Day 210

The proportion of patients with a new or recurrent BILAG A flare or  $>1$  BILAG B flares through Day 210 will be summarized by study phase and treatment group in the FAS. Statistical methods described in Section 7.1.1 will be implemented. BILAG flares will be adjudicated, recorded in the clinical database, and summarized as recorded in the clinical database. Flare assessments will be performed on BILAG grades whether or not designation of a BILAG grade required carrying component data forward by the assessor. However, no LOCF methods will be implemented with respect to flare data itself. When discrepancies between the two-reviewers occurs, the adjudicated flare determination will be used for analyses. The proportion of new or recurrent BILAG A flare or  $>1$  BILAG B flare will be summarized overall and by nominal visit. The denominator for percentages of patients with a new or recurrent flare will be patients in the FAS with a post-baseline BILAG assessment at the given visit.

Statistical testing data will be omitted from MAD Phase 1b treatment group displays.

Sponsor: Boston Pharmaceuticals, Inc.  
Protocol Number: BOS161721-02  
SAP Version and Date: Version 4.0, 23Apr2021

Results as recorded in the clinical database will be presented in separate data listings for BILAG SLE history, BILAG-2004 index, and BILAG grading for all randomized patients.

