## 2.2. Proof of Concept (POC) Phase 2 Study

| Objectives       | Endpoints  |
|------------------|--|
| Primary   | 
Primary Efficacy Endpoint
 
 
The proportion of patients with a SRI-4 response at Day 210
 
   |
| Secondary | 
Secondary Efficacy Endpoints
 
 
The proportion of patients with:             
 
- SRI-4 response at each visit
 
- SRI-5 and SRI-6 response at each visit
 
- a sustained reduction of oral corticosteroid (CS) (<math>\leq 7.5</math> mg/day and <math><</math> Day 0 dose) between Day 150 and Day 210
 
- new or recurrent BILAG flares (<math>\geq 1</math> qualifying BILAG A or <math>> 1</math> qualifying BILAG B) through Day 210
 
- PGA worsening
 
- a BICLA response
 
- a CLASI response
 
- medication failures
 
 
 
Change and percentage change from baseline at each visit in:             
 
- CLASI
 
- PGA
 
- Total number of swollen joints, tender joints, and active joints (swelling and tenderness in the same joint) in the ACR-28 joint count
 
- SLEDAI-2K
 
- SLICC/ACR damage index
 
 
 
TTMF
 
Group mean percent reduction in corticosteroid administration from baseline Day 0 dose through Day 210 in patients receiving <math>\geq 7.5</math> mg/day prednisone equivalent at Day 0
 
 |

Sponsor: Boston Pharmaceuticals, Inc.  
Protocol Number: BOS161721-02  
SAP Version and Date: Version 4.0, 23Apr2021

| Objectives | Endpoints  |
|------------|--|
|            | 

• Duration of longest SRI-4 response

• Time to first BILAG flare (<math>\geq 1</math> new or recurrent BILAG A or <math>> 1</math> new or recurrent BILAG B) relative to baseline through Day 210

   |

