**Evaluability/Non-Responders:**

**Medication Failures:** Patients who received prohibited medications or undergo unallowable corticosteroid (CS) usage will be considered “medication failures” and will be treated as non-responders at time points on and following the first date of prohibited medication or unallowable CS usage for the primary efficacy analysis. Prohibited medications are detailed in Appendix 4 of the study protocol. Prohibited medications and unallowable CS usage will be recorded as protocol deviations in the clinical database.

A patient is considered to have unallowable CS usage if any of the following is not met:

- A maximum daily dose of 30 mg/day of oral CS will be acceptable for eligibility for the study. For patients whose only SLE treatment is steroids, their stable steroid dose must be at least 10 mg/day and no more than 30 mg/day for a minimum of 6 weeks at time of randomization on Day 0
- Topical steroids may be used, but the dose must be stable for at least 6 weeks prior to Day 0, and be maintained at a constant dose throughout the study duration until the rashes resolve. PRN topical steroids are not permitted
- Once the patient has received the first dose of study drug (Day 0), tapering of oral steroids will be highly encouraged and should be continually evaluated during the protocol-allowed tapering windows (Day 0 through Day 150) with the target of achieving a CS daily dose of < 7.5 mg and < Day 0 dose between Day 150 and Day 210
- Between Day 150 and Day 210 (i.e., within 60 days of primary endpoint assessments), oral CS doses must be held constant
- CS Burst for SLE-related Indications
  - After Day 0 (first dose of study drug), a maximum of 1 oral CS “burst” equivalent to  $\leq$  40 mg/day prednisone for increased SLE disease activity will be allowed between Day 0 and Day 120, which must be tapered down to the baseline (Day 0) CS dose or lower within 14 days of initiation of the “burst”. Any “burst” continuing after Day 120 or occurring after Day 120 is considered a protocol deviation.
  - Alternatively, a single intramuscular (IM) dose of methylprednisolone ( $< 40$  mg) is permitted during this period.
- CS Burst for Non-SLE-related Indications
  - A single treatment of oral prednisone equivalent of  $\leq$  40 mg/day for 14 days is permitted for a non-SLE indication, though it must be completed prior to Day 120. No long acting steroid injections are permitted.

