  - Note: Treatment with inhaled CS are allowed for the treatment of non-SLE-related indications only (e.g., for asthma).

Sponsor: Boston Pharmaceuticals, Inc.  
Protocol Number: BOS161721-02  
SAP Version and Date: Version 4.0, 23Apr2021

Any other increase from baseline of CS dose or any other systemic use of CS of any kind (including intra-articular and intravenous administration) are not permitted from Day 0 through Day 210 and will result in the patient being considered a medication failure and will be treated as non-responders for the primary efficacy analysis. There is no restriction of CS usage after Day 210.

The determination of medication failures will be reviewed using blinded data and finalized prior to unblinding. Once a patient is determined to be a non-responder, the patient will remain a non-responder for the remainder of the study.

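### The only planned analysis of percent corticosteroid reduction drops patients once they become medication failures, and an unpermitted rise in corticosteroid dose is one cause of that failure

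*SAP*

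**What the plan says.** Section 2.2 of the SAP lists as a POC secondary efficacy endpoint the "Group mean percent reduction in corticosteroid administration from baseline Day 0 dose through Day 210 in patients receiving" at least 7.5 mg/day prednisone equivalent at Day 0. Section 7.2.4.3 summarizes it by treatment group and visit in the FAS and adds: "Patients considered medication failures will be excluded from the percent reduction analysis at timepoints on and after the first date of medication failure". No alternative or sensitivity version is given.

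Medication failure is defined in Section 7.1.1 under Evaluability/Non-Responders: "Patients who received prohibited medications or undergo unallowable corticosteroid (CS) usage will be considered" medication failures. There are therefore two routes, prohibited medication and unallowable CS use. The second route includes this: "Any other increase from baseline of CS dose or any other systemic use of CS of any kind" is not permitted from Day 0 through Day 210 and "will result in the patient being considered a medication failure". It also covers the topical steroid conditions and the rule that between Day 150 and Day 210 "oral CS doses must be held constant".

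Section 7.2.4 builds the dose at a visit from "the sum of the corticosteroid doses taken each day from the date of the previous visit" to the day before the current visit, divided by the length of that interval.

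Section 7.2.4.2, on sustained CS reduction, says that patients designated as medication failures on or before Day 210 "will not be considered to have sustained reduction in CS". They stay in its denominator.

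**The concern.** The endpoint averages CS dose. For a patient who fails because the dose rose, the event that triggers exclusion is a bad value of that same outcome. The group mean at each later visit then describes only patients who have not yet failed, which is narrower than the population named in Section 2.2. These are not missing data: the daily doses are recorded and are used in other sections.

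What is at stake is the meaning of a listed secondary endpoint. If failures reduce less than other patients, both arm means look better than they were. If the arms also fail at different rates, the steroid-sparing comparison is distorted.

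**Working it through.** **Figures in the plan.** The SAP states no expected failure rate, CS dose change or power for this endpoint, so there is nothing to reproduce. Its only design calculation (96 evaluable patients, Section 3.3) concerns SRI-4 and has no bearing here.

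**Step 1: how much is removed.** The dose at a visit averages the interval that ends the day before. A rise that starts on the failure date first enters the average at the next visit, and that visit is already excluded. No dose taken from the failure date onward can enter the endpoint.

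**Step 2: handling elsewhere in the SAP.**
- Section 7.2.4.2 keeps failures and counts them as not reduced. Its denominator is all patients on oral CS at baseline, so it overlaps with the group on at least 7.5 mg/day but is not identical to it.
- Section 7.2.6.2 (PGA) has an Approach 1, matched to the primary analysis, that retains failures by carrying forward the last value before failure. Exclusion appears only as Approach 2, matched to Sensitivity Analysis 2. CLASI, ACR-28 and SLEDAI-2K also use the two approaches (the last two cite 7.2.6.1, although the approaches stand in 7.2.6.2).
- Section 7.2.4.3 has exclusion alone.

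**Step 3: size.** Let f be the proportion of eligible patients in an arm who have failed by a visit, R the mean percent reduction in non-failures, and r that in failures (negative if the dose rose).

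- Mean with everyone kept: (1 − f) × R + f × r
- Mean under the SAP rule: R
- Overstatement: f × (R − r)

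All values below are assumptions: R = 30% in both arms, f = 15% active and 35% placebo. The SAP rule shows 30% vs 30%, a difference of 0.

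| Failures' dose change | Active, all kept | Placebo, all kept | Difference hidden |
|---|---|---|---|
| none (r = 0) | 0.85×30 = 25.5 | 0.65×30 = 19.5 | 6 points |
| +25% (r = −25) | 25.5 − 3.75 = 21.75 | 19.5 − 8.75 = 10.75 | 11 points |
| +50% (r = −50) | 25.5 − 7.5 = 18 | 19.5 − 17.5 = 2 | 16 points |
| +100% (r = −100) | 25.5 − 15 = 10.5 | 19.5 − 35 = −15.5 | 26 points |

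The overstatement with r = 0 is 0.15×30 = 4.5 points (active) and 0.35×30 = 10.5 points (placebo). With r = −50 it is 0.15×80 = 12 and 0.35×80 = 28.

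**Step 4: dependence on the assumed rates.**
- With 15% vs 30% failures, the hidden difference is 0.15 × (30 − r): 4.5, 8.25, 12 and 19.5 points for the same four rows.
- With 20% in both arms and the same r, the difference stays 0. The true mean in each arm is 24%, 19%, 14% or 4%, while the rule shows 30%.
- With the rates swapped (35% active, 15% placebo), the same 6 to 26 points would be a hidden disadvantage of the active drug.
- If failures reduced more than non-failures, for instance r = 50 with f = 15%, the mean would be understated by 0.15 × 20 = 3 points.

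**The case against.** A CS rise is only one route to failure. Prohibited medication and topical steroid changes are others, and on its wording the Day 150 to Day 210 rule is breached by a dose cut as well as by a rise. Permitted bursts are not failures and remain in the analysis. A reader might infer that every excluded patient is a bad steroid outcome; the SAP does not support that, and it does not say how large the subset is. This part of the objection stands.

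A reader might also infer that placebo would have more failures, or that the comparison would be reversed. The SAP gives no failure rates by arm, so neither can be claimed. In the illustration with more placebo failures, the rule works against the active drug and creates no false benefit.

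Related information is shown elsewhere. Section 6.6 summarizes average daily prednisone-equivalent dose by visit with no stated exclusion, and Sections 7.2.12.1 and 7.2.12.2 report the proportion of failures and the time to failure. A reader of the full report would therefore see escalation. But Section 6.6 uses the safety set, is not a percent reduction and is not limited to patients on at least 7.5 mg/day, so none of these corrects the endpoint.

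Section 7.2.4.3 names no test, which limits its inferential weight. Exclusion also has a precedent: Approach 2, and the SLICC/ACR index in Section 7.2.11, where failures before Day 180 are not evaluable. Results up to failure answer a recognizable question. That supports keeping the exclusion version, though not as the only one.

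Finally, retaining actual doses for every failure could credit steroid sparing to a patient who started a prohibited drug and then lowered steroids. That is a sound point, and the fix takes it up.

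**Conclusion.** The point holds in a limited form. The sole analysis of a listed secondary endpoint excludes recorded doses, and for patients who fail through an unpermitted CS rise the exclusion depends on the outcome being averaged. It is also inconsistent with Section 7.2.4.2 and with the two-approach pattern used for PGA, CLASI, ACR-28 and SLEDAI-2K.

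Each arm's mean is overstated by f × (R − r) whenever failures reduce less than non-failures. That condition is plausible where failure is due to a rise, but the SAP does not guarantee it for failures as a whole. The between-arm effect has no fixed sign or size. The 6 and 16 points at 15% vs 35% failures rest entirely on assumed rates, dose changes and equal reductions in non-failures. The primary endpoint is not affected. The section should be changed because the change is cheap and the present rule leaves the endpoint hard to interpret.

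**What to change.** Reword Section 7.2.4.3 so that the main summary retains medication failures through Day 210:

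- for failures due to CS use, use the recorded average daily prednisone-equivalent dose, calculated as in Section 7.2.4;
- for failures due to prohibited medication, count the result as no better than no reduction, that is, the smaller of the recorded percent reduction and zero, in line with Section 7.2.4.2;
- keep the present exclusion version as a supplementary summary, parallel to Approach 2 in Section 7.2.6.2.

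Approach 1 should not simply be copied. Carrying forward the last dose before failure would keep the patient but still hide the rise.

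This changes the analysis only. It needs no new data and does not touch patient management. The cost is revised SAP wording and one more summary, and the displayed mean reductions will probably be smaller.

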## 7.2.6. Physician's Global Assessment (PGA)

The PGA is used to assess investigator's general impression on the patient's overall status of SLE disease activity via visual analogue scale (100 mm) with 0 being "very good, asymptomatic and no limitation of normal activities" with 100 mm being "most severe possible disease ever seen in all SLE patients."

### 7.2.6.1. Proportion of Patients with PGA Worsening at Each Visit

The proportion of patients with PGA worsening, defined as an increase of  $\geq 30$ mm from baseline, will be summarized by study phase and treatment group in the FAS overall (at any post-baseline nominal visit) and by nominal visit. Statistical methods described in Section 7.1.1 will be implemented. In case of missing data, LOCF methods will be implemented as described in section 5.4 and Table 1 and in Section 7.2.1 for the "at each visit" analyses.

The analyses described in Section 7.1.1 and Table 2 (Primary Analysis methods) will be repeated for each nominal visit as described in Section 7.2.1 based on the PGA worsening definition and will be presented by study phase and treatment group in the FAS.

The denominators for analyses will be the number of patients in the FAS with an evaluable post-baseline PGA assessment (overall analysis) or with evaluable PGA assessment (whether or not imputed via LOCF depending on the analysis) at a given visit (nominal visit analysis).

Statistical testing data will be omitted from MAD Phase 1b treatment group displays.

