**Table 2**

| Analysis   | Analysis Population | Criteria   |
|--|---------------------|--|
| Primary Analysis

LOCF for missing data,
Medication
Failures=Non-Responder | FAS                 | 
The primary analysis of the primary efficacy endpoint will be performed based on LOCF methods for missing data.
 
 
(1) Medication failures are considered non-responders on and after the date of medication failure
 
(2) Early withdrawals/discontinuations prior to study day 159 will be considered non-responders after the date of early withdrawal/discontinuation
 
 |

|  |     |  |
|--|-----|--|
|  |     | 
 
a. If patient is a medication failure prior to withdrawal/discontinuation, patient will be considered a non-responder on and after the date of medication failure.
 
b. In case of early withdrawal/discontinuation after study day 159 but before Day 210 such that patient has Day 180 data but is lacking Day 210 data in a patient without medication failure, the Day 180 data will be carried forward to Day 210.
 
 
(3) Patients with missing Day 180 and Day 210 data without prior medication failure and without early withdrawal/discontinuation prior to study day 159 are considered not evaluable and are excluded from analysis
  |

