### 7.2.1. Proportion of Patients with SRI-4 Response at Each Visit

The primary analysis methods described in Section 7.1.1 and Table 2 will be repeated for each nominal visit and will be presented by study phase and treatment group in the FAS. Other analyses described in Section 7.1.1 may also be performed. The 3 components will not be summarized separately by visit. In case of missing data, LOCF methods will be implemented as described in section 5.4 and Table 1. LOCF will only be implemented with the most recent prior nominal visit. If the most recent prior nominal visit is missing, occurred more than 30 days before, or is not evaluable, LOCF is not implemented. For example, if Day 30 SLEDAI assessment is complete but Day 60 and Day 90 SLEDAI assessments are missing, Day 60 will implement LOCF from Day 30 assuming Day 30 is within 30 days of Day 60 and Day 60 SLEDAI will be included in the analysis but Day 90 will not carry forward from Day 60 and thus Day 90 will be considered not evaluable and will be excluded from the analysis. Similarly, if Day 150 assessments are complete but Day 180 and Day 210 are missing, Day 180 will implement LOCF from Day 150 assuming Day 150 is within 30 days of Day 180 and will be included in the analysis but Day 210 will not carry forward from Day 180, will be considered not evaluable, and will be excluded from the analysis.

Sponsor: Boston Pharmaceuticals, Inc.  
Protocol Number: BOS161721-02  
SAP Version and Date: Version 4.0, 23Apr2021

If a patient is a medication failure, the patient is considered to be a non-responder at timepoints on or after the first date of prohibited medication/unallowable CS usage.

If a patient discontinues/withdraws early, the patient will be considered a non-responder after the date of discontinuation/withdrawal (unless the patient had a prior medication failure in which case the patient is considered a non-responder on and after the date of medication failure).

The denominators for analyses will be the number of patients in the FAS with an evaluable post-baseline SRI-4 assessment defined as those with data for PGA, SLEDAI-2K and BILAG (whether observed or imputed via LOCF depending on the analysis) at a given visit.

A graphical display of SRI-4 response by study phase, treatment group, and visit in the FAS will be presented.

Statistical testing data will be omitted from MAD Phase 1b treatment group displays.

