#### 7.2.13. Duration of Longest SRI-4 Response

Duration of longest SRI-4 response will be computed for patients who have been identified as a responder at least once based on criteria defined in Section 7.1.1 utilizing LOCF methods consistent with the primary efficacy analysis. The duration of longest response will be defined as the longest period a patient meets the SRI-4 responder criteria at consecutive visits. This will be computed as the date of last consecutive SRI-4 response – date of first consecutive response + 1. If the last consecutive response is based on LOCF methods and the last consecutive response does not have a date, duration of longest SRI-4 Response will be computed as the (date of last non-missing consecutive SRI-4 response + 30) – date of first consecutive response + 1.

The duration of longest SRI-4 response will be analyzed using an analysis of variance (ANOVA) model with treatment group as the effect. The p-value for the difference between the BOS161721 and placebo group is based on the F-test.

The mean, SD, median, minimum, maximum, Q3, Q4, LS Mean estimate, its standard error and 90% CI will be tabulated by treatment group and for the difference between treatment groups (BOS161721 versus placebo).

If a patient has missed a visit between two scheduled visits with a response at both, the patient will be counted as having a response at the missed visit unless otherwise specified.

Duration of longest SRI-4 response will be displayed in the SRI response listing.

These analyses will also be performed for the MAD Phase 1b with the exception of the statistical testing.

#### 7.2.14. Time to First BILAG A Flare or >1 BILAG B Flare through Day 210

Time to first BILAG A Flare or >1 BILAG B Flare will be computed as the event date (as described below) – randomization date + 1. If a patient is designated as a medication failure prior to or on their day 210 visit, they will be considered as having a BILAG flare (event) as of the date of first dose of the medication leading to the medication failure designation due to prohibited medication or unallowable CS burst.

Time to first BILAG A Flare or >1 BILAG B Flare will be analyzed with Kaplan-Meier methods described for TTMF and censoring as described in Table 5. Kaplan-Meier curves will be plotted over time.

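### By-visit PGA worsening reuses the responder rules without reversing them, so a medification failure who stays in the study counts as not worsened even with a recorded rise of 30 mm or more

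*SAP*

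**What the plan says.** In SAP Version 4.0, Section 7.2.6.1 introduces the endpoint as "The proportion of patients with PGA worsening, defined as an increase of" at least 30 mm from baseline, summarised by nominal visit and at any post-baseline visit. For the by-visit analysis it states "Primary Analysis methods) will be repeated for each nominal visit as described in Section 7.2.1 based on the PGA worsening definition". The by-visit denominator is the FAS patients with an evaluable PGA at that visit, observed or carried forward.

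The imported rules are these:

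- Table 2, primary analysis, item 1: "Medication failures are considered non-responders on and after the date of medication failure".
- Table 2, primary analysis, item 2: "Early withdrawals/discontinuations prior to study day 159 will be considered non-responders after the date of early withdrawal/discontinuation". If withdrawal comes later than that but before Day 210, and Day 180 data exist, those data are carried forward to Day 210.
- Section 7.2.1, for by-visit analyses: "If a patient discontinues/withdraws early, the patient will be considered a non-responder after the date of discontinuation/withdrawal". No study-day limit is given here.
- Section 7.1.1, under medication failures: "Once a patient is determined to be a non-responder, the patient will remain a non-responder for the remainder of the study".

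Section 7.1.1 also repeats the Day 210 analysis for each of the three SRI-4 components. One of them is the absence of a PGA deterioration of 30 mm or more.

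**The concern.** The non-responder rule is conservative only when meeting the definition is good. That is so for SRI-4, SRI-5, SRI-6, BICLA and CLASI response. PGA worsening runs the other way. If its definition is put into Table 2, a non-responder is someone who does not meet the worsening definition, and nothing in Section 7.2.6.1 reverses the coding.

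The plainest case is a medication failure who stays in the study and has a PGA recorded at later visits. A rise of 30 mm or more at such a visit would be replaced by no event. This is not a missing-data question, because a recorded bad outcome is overwritten.

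At stake is a secondary endpoint tested at the SAP's 10% level. Its rate would be too low in both arms, and its treatment difference would be pulled in favour of whichever arm has more failures.

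**Working it through.** The SAP states no rate for PGA worsening or for medication failure, so there is no planned figure to reproduce. The check is a trace of the rules followed by an illustration.

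**Trace at Day 210.** Take a patient who became a medication failure on Day 100, stayed in the study, and has a Day 210 PGA 35 mm above baseline (a hypothetical case).

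- PGA component of SRI-4 (Section 7.1.1): the failure rule makes the patient a non-responder, which is the unfavourable side.
- PGA worsening (Section 7.2.6.1): the same rule makes the patient a non-responder, which is the favourable side.

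The two results should be complements. Let f be the proportion of failures and w the worsening rate among other patients. The component is met by (1 - f)(1 - w) and worsening by (1 - f)w. These sum to 1 - f, not 1, so the failures are missing from both event counts.

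**Illustration.** The inputs are assumptions: f = 15% on BOS161721 and 30% on placebo, w = 5% in both arms, v = 40% of failures truly worsened, and every patient in the denominator. Differences are BOS161721 minus placebo, so a negative value favours BOS161721.

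- Literal rule, (1 - f)w: 0.85 × 5% = 4.25%; 0.70 × 5% = 3.5%; difference +0.75 points.
- Observed PGA kept, (1 - f)w + fv: 4.25% + 0.15 × 40% = 10.25%; 3.5% + 0.30 × 40% = 15.5%; difference -5.25 points.
- Failure placed in the unfavourable category, (1 - f)w + f: 4.25% + 15% = 19.25%; 3.5% + 30% = 33.5%; difference -14.25 points.

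**Range**, with w = 5% throughout (differences in points):

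| Failures, BOS161721 / placebo | Literal rule | Observed PGA, v = 20% | Observed PGA, v = 40% | Failure unfavourable |
|---|---|---|---|---|
| 10% / 20% | +0.5 | -1.5 | -3.5 | -9.5 |
| 15% / 30% | +0.75 | -2.25 | -5.25 | -14.25 |
| 20% / 40% | +1.0 | -3.0 | -7.0 | -19.0 |

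With w equal in the arms, the literal difference is w times (placebo f minus BOS161721 f), so the arm with more failures always looks better. With failures of 10% in both arms the difference is zero under every coding. The literal rate is then 4.5% in each arm, against 6.5% to 8.5% with observed PGA kept and 14.5% with failures unfavourable.

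**The case against.** The strongest reply is that the SAP nowhere says not worsened. A programmer could take non-responder to mean the unfavourable category, in which case the coding is undefined and not reversed. It is true that the words are absent. But the opposite coding is not written either, and the rule applied as it stands gives the reversed result. Elsewhere the SAP does adapt its handling: continuous PGA in Section 7.2.6.2 uses carry-forward or exclusion, and time to flare counts a failure as an event.

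Several wider readings are tempting, and the document does not support them:

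- *All withdrawals count as not worsened.* The by-visit denominator needs an evaluable PGA, so a withdrawn patient without one may leave the analysis. Withdrawals on or after study day 159 with Day 180 data are carried forward to Day 210.
- *The any-visit analysis has the same fault.* Section 7.2.6.1 ties Table 2 to the nominal visits. The any-visit summary is not expressly tied to it, and worsening before a failure would still count there.
- *The worst outcomes are counted as good.* Under Section 7.1.1 a medication failure can arise from as-needed topical steroid use or from an oral steroid dose not held constant between Day 150 and Day 210. Neither requires a PGA rise.
- *The flare proportion in Section 7.2.5 repeats the error.* That section never invokes Table 2: "BILAG flares will be adjudicated, recorded in the clinical database, and summarized as recorded in the clinical database". Section 7.2.14 openly defines a different quantity, because patients who fail on medication by Day 210 are included: "they will be considered as having a BILAG flare (event) as of the date of first dose". These are two stated definitions, and a rescued patient with a recorded flare is counted in both.

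It is also fair that medication failures are reported by arm (Section 7.2.12) and continuous PGA is analysed in two ways, so an imbalance in failures would be visible. That helps a reader interpret a wrong table but does not correct it.

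**Conclusion.** The point holds for the by-visit PGA worsening proportion, and most clearly for medication failures who remain in the study with PGA recorded. Applied literally, the rule removes observed deterioration, understates worsening in both arms, favours the arm with more failures, and disagrees with the Day 210 PGA component of SRI-4. For early withdrawals the effect is uncertain until the denominator is settled.

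The size cannot be taken from the SAP. Over the assumed range, with placebo failures twice those on BOS161721, the literal rule gives +0.5 to +1.0 points where observed PGA would give -1.5 to -7.0. The change of sign rests on that imbalance, on equal worsening among the other patients, and on failures worsening more often than they do. Which arm will have more failures is not known from the document.

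This is a secondary endpoint, and the primary SRI-4 analysis is unaffected. The coding should still be corrected before unblinding, because the cost is small.

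**What to change.** In Section 7.2.6.1, state that Table 2's non-responder rule is reversed for this endpoint:

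- Medication failures take the unfavourable category on and after the failure date. Withdrawals before study day 159 take it after withdrawal.
- Table 2's carry-forward from Day 180 to Day 210 is kept, and Table 2's study-day limit governs in place of the unlimited wording in Section 7.2.1.
- Patients classified by these rules stay in the by-visit denominator whether or not a PGA was recorded.
- The row is labelled as PGA worsening or medication failure/withdrawal, since it is then a composite.
- A second version uses the observed PGA regardless of medication failure.

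The cost is a few lines of text and one programming flag. Rates rise in both arms, and some failures without a PGA rise are counted as events. In the 15% / 30% illustration most of the -14.25 points is simply the 15-point gap in failures. The label and the observed-PGA version are there to make that visible.

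The flare proportion in Section 7.2.5 should not be redefined. At most, a footnote can say that it counts recorded flares only, while Section 7.2.14 analyses flare or medication failure.
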